5.1 Study treatment

5.1.1 Investigational and control drugs

The Study drug is as follows:

• QMF149 (indacaterol acetate/MF) 150/80 microgram o.d. (in the evening) delivered as powder in hard capsules via Concept1 inhaler

The Comparative treatment is:

• MF 200 microgram o.d. (in the evening) delivered as powder via Twisthaler®

In addition, the following placebos will enable the double-dummy design of the study:

- Placebo delivered as powder via Twisthaler[®] (in the evening)
- Placebo delivered as powder in capsules via Concept1 (in the evening)

Page 33

5.1.2 Additional treatment

The specified minimum washout periods prior to Run-in (Visit 101) are described in Table 5-1. The low dose fluticasone propionate (100 microgram b.i.d. via Accuhaler or 125 microgram b.i.d via MDI) should be used during the Run-in epoch. If these are not available in a particular country, fluticasone propionate in an alternative formulation at an equivalent dose strength can be used (Appendix 9). These will either be supplied to the investigator sites locally by Novartis or provided by the study center and reimbursed by Novartis.

At Visit 1 (Screening) patients will be provided with SABA (salbutamol/albuterol) inhaler to use as rescue medication on an "as needed" basis throughout the study. Please refer to Section 5.5.6 for more details regarding rescue medication.

Salbutamol (100 microgram) or albuterol (90 microgram) will either be supplied to the investigator sites locally by Novartis or provided by the study center and reimbursed by Novartis.

5.2 **Treatment arms**

Patients will be assigned to one of the following two treatment arms (as per randomization ratio of 1:1):

- QMF149 150/80 microgram o.d. delivered via Concept1 (in the evening) and Placebo to MF 200 microgram o.d. delivered via a Twisthaler[®] (in the evening)
- MF 200 microgram o.d. delivered via a Twisthaler® (in the evening) and Placebo to QMF149 150/80 microgram o.d. delivered via Concept1 (in the evening)

5.3 Treatment assignment and randomization

At Visit 201, all eligible patients will be randomized via Interactive Response Technology (IRT) to one of the treatment arms. The investigator or his/her delegate will contact the IRT after confirming that the patient fulfills all the inclusion/exclusion criteria. The IRT will assign a randomization number to the patient, which will be used to link the patient to a treatment arm and will specify a unique medication number for the first package of study drug to be dispensed to the patient. The randomization number will not be communicated to the caller.

The randomization numbers will be generated using the following procedure to ensure that treatment assignment is unbiased and concealed from patients and investigator staff. A patient randomization list will be produced by the IRT provider using a validated system that automates the random assignment of patient numbers to randomization numbers. These randomization numbers are linked to the different treatment arms, which in turn are linked to medication numbers. A separate medication list will be produced by or under the responsibility of Novartis Drug Supply Management using a validated system that automates the random assignment of medication numbers to packs containing the investigational drug(s).

Randomization will be stratified by factors of age (≥ 12 to ≤ 18 years or ≥ 18) and by region.

The randomization scheme for patients will be reviewed and approved by a member of the Randomization Group.

5.4 Treatment blinding

Patients, investigator staff, persons performing the assessments, and data analysts will remain blind to the identity of the treatment from the time of randomization until database lock, using the following methods:

- Randomization data are kept strictly confidential until the time of unblinding, and will not be accessible by anyone (with the exception of bio-analyst) involved in the study
- The identity of the treatment will be concealed by the use of study drugs that are all identical in packaging, labeling, and schedule of administration, appearance, taste, and odor.

During the study, the individual patient unblinding can occur in the case of patient emergencies, request from the DMC if needed for the safety interim analysis (Section 8.4) or as an outcome of their evaluation and at the conclusion of the study. Health authorities will be granted access to unblinded data if needed. Any patient whose treatment code has been broken inadvertently or for any non-emergency reason will be discontinued from the trial.

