5.6 Study completion and discontinuation

5.6.1 Study completion and post-study treatment

Completion of the study will be when the last patient has completed Visit 301 and as close as possible to safety follow-up at Day 114 for serious adverse events (SAEs).

The investigator must provide follow-up medical care for all patients who are prematurely withdrawn from the study, or must refer them for appropriate ongoing care.

5.6.2 **Discontinuation of study treatment**

Patients may voluntarily discontinue study drug (discontinue double-blind study medication but continue with study participation) at any time. Patients who wish to discontinue double-blind study medication will be asked to remain in the study and complete all study visits for

assessment of safety and vital status. Patients withdrawn from study drug will receive standard of care (SoC) asthma therapy according to investigator judgment.

The investigator should discontinue study treatment for a given patient and/or withdraw the patient from the study if, on balance, he/she believes that continuation would be detrimental to the patient's well-being.

Study treatment must be discontinued under the following circumstances:

- Patients who experience one "severe" asthma exacerbations (as defined in Section 6.4.9) during the 12 week treatment epoch that requires treatment with systemic corticosteroids or hospitalization (including intubation).
- Patients with > 50% decrease in FEV₁ from Baseline (e.g., Visit 101) confirmed by a repeat measurement the same day during the Run-in or during the treatment epoch (Baseline being then Visit 201).
- If a patient develops a medical condition that requires consistent use of prohibited treatment as per Section 5.5.8 or if patient is not compliant because of use of prohibited medications. Any other protocol deviation that results in a significant risk to the patient's
- If a patient experiences paradoxical bronchospasm, as recommended in the QMF149 **Investigator Brochure**
- Any other protocol deviation that results in a significant risk to the patient's safety.

Discontinuation of study treatment (but continued study participation)

For this study it is very important to continue collecting data, especially vital status, on all patients whether or not he/she completes treatment to continue collecting safety information. The patient should NOT be considered withdrawn from the study due to study treatment interruption or discontinuation.

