If premature discontinuation of study treatment occurs, the patient should return to the clinic as soon as possible for a study Treatment Discontinuation (TD) visit. The investigator must determine the primary reason for the patient's premature discontinuation of study treatment and record this information on the End of Study Treatment eCRF. The investigator and study staff must discuss with the patient the continued participation in the study by maintaining regular telephone contact with him/her or with a person pre-designated. This telephone contact should preferably be done according to the study visit schedule.

The data which must continue to be collected for all patients (including the patients discontinuing study treatment) are adverse event and serious adverse events for up to 30 days after drug discontinuation and survival status until the end of the study follow-up visit (Visit 301).

Any patient whose treatment code has been broken inadvertently or for any non-emergency reason should be discontinued from the double blind study medication. Patients can voluntarily stay in the study and complete all study visits for assessment of safety and vital status. The survival status also needs to be collected until the end of the study Follow-up visit (Visit 301)

Patients who discontinue study treatment should NOT be considered withdrawn from the study. He/she should return for the assessments indicated in Table 5-4. If he/she fails to return for these assessments for unknown reasons, every effort (e.g., telephone, e-mail, and letter) should be made to contact them as specified in Section 5.6.4.

The investigator must also contact the IRT to register the patient's discontinuation from study treatment.

Table 5-4 Table of Assessment for Patients who Discontinue Study Treatment Prematurely

Assessment	Early Study Treatment Discontinuation Visit	Unschedule d Safety Follow-Up Visit	At time of Scheduled Visit	Premature study discontinuation	Follow- up Visit 301
Clinic/Telephone	С	T	Т	Т	Т
Week	Disc. Date	Disc.date +4 weeks			16
Day	Disc. Date	Disc.date +30 days			114
IRT TD call	S				
IRT Call for visit confirmation	S		S	S	S
Vital Signs	X				
Physical exam	S				
Record Height (Adolescent only)	X				
Record Weight	Х				
Oropharyngeal examination	S				
Pregnancy test (serum)	X				
Collect study medication	S				
Concomitant medication	X	Х	Х	Х	X
Record interruption/chang es in Drug Administration to assess compliance	X				
Download/review eDiary	S				

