Review rescue medication use	S				
Review AEs	X	X	Χ	X	Χ
Review SAEs	X	Х	Χ	X	Χ
Review asthma exacerbations	X	Х	X	X	

Assessment	Early Study Treatment Discontinuation Visit	Unschedule d Safety Follow-Up Visit	At time of Scheduled Visit	Premature study discontinuation	Follow- up Visit 301
Review surgery and procedures	X	X	X	X	X
Safety Lab assessments (hematology, clinical chemistry, urinalysis,	X				
Spirometry ¹	X				
ECG	Χ				
ACQ-7 ²	X				
Evening Plasma cortisol	X				
Survival Status		X			Χ
Record Healthcare visit for asthma worsening	X			X	
Record end of Study Treatment page	Х				
Record end of treatment epoch disposition				Х	

S These assessments are source documentation only and will not be entered into the eCRF

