## **2.3 Patient disposition, demographics and other baseline characteristics**

### **2.3.1 Patient disposition**

The number of patients will be summarized by region (i.e., Eastern Europe, Western Europe, India, Japan, Asia (other than India and Japan), rest of world), country and treatment group for the RAN set. Further, for each study epoch (i.e., screening, run-in, treatment phase, post treatment follow-up), the overall number of patients who entered, completed, and discontinued that phase will be summarized including the reasons for discontinuation.

Time to premature treatment discontinuation will be displayed graphically for each treatment group using a Kaplan-Meier curve for the safety analysis set. The date of premature treatment discontinuation is defined as the date of last dose of study treatment. Patients who completed the study treatment will be censored at the date of last dose of study treatment.

Number of patients with protocol deviations will be tabulated by deviation category (e.g., selection criteria not met, prohibited concomitant medication).

The number of patients included in each analysis set will be tabulated, as well as the reasons for exclusions from analysis sets.

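### Protocol Sections 5.4 and 5.6.2 prescribe incompatible consequences for the same inadvertent or non-emergency code break: leave the trial, or stop study drug and stay in follow-up

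*Protocol*

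**What the plan says.** Protocol 5.4 (Treatment blinding) closes with the rule "Any patient whose treatment code has been broken inadvertently or for any non-emergency reason will be discontinued from the trial".

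Protocol 5.6.2 (Discontinuation of study treatment) covers the same event in nearly the same words: "Any patient whose treatment code has been broken inadvertently or for any non-emergency reason should be discontinued from the double blind study medication". It continues: "Patients can voluntarily stay in the study and complete all study visits for assessment of safety and vital status". It then requires survival status until the follow-up visit, Visit 301. The same section explains why it retains patients: "it is very important to continue collecting data, especially vital status, on all patients whether or not he/she completes treatment". It also says twice that stopping study treatment is not withdrawal from the study.

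Three other places mention a broken blind. Protocol 5.5.5 and 5.5.9 require study medication to stop. SAP 6.7, deviation WTH06A, excludes a patient from the per-protocol set if the blind was broken and treatment was not stopped. None of the three says whether the patient stays in the trial.

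**The concern.** The two sentences share a trigger, so they cannot be assigned to different situations. One orders the patient out of the trial. The other stops the drug and keeps the patient under observation. An investigator facing a code break has two instructions and no rule of precedence, and the stricter wording (a mandatory exit) is in the section on blinding, where a site is likely to look first.

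What is at stake is safety and survival follow-up and the recording of disposition for these patients. It is not the treatment comparison.

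**Working it through.** There is no plan figure to reproduce; this is a comparison of texts followed by one piece of date arithmetic.

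**Step 1: the instructions side by side**

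| Item | Following 5.4 literally | Following 5.6.2 |
|---|---|---|
| Double-blind drug | Stopped | Stopped |
| Participation | Ends | May continue, voluntarily |
| Scheduled contacts (Days 30, 57, 84) | Dropped | Made by telephone, with AE and SAE review (Table 5-4) |
| Survival status to Visit 301 | Omitted | Required |
| Study exit recorded | Possibly | No |

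**Step 2: which text is out of line.** Section 5.6.2 is the operative section on discontinuation, states its aim of retaining patients, and separates stopping drug from leaving the study. Sections 5.5.5 and 5.5.9 and WTH06A are compatible with it but silent on participation. Section 5.4 alone ends participation, so it is the text to correct.

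**Step 3: survival follow-up lost.** Inputs: Visit 301 is on Day 114 (Tables 5-4 and 6-1). Safety follow-up runs for 30 days after the later of last dose and last visit (Protocol 3.6 and 7.2.2). Suppose this 30-day follow-up is still done under 5.4. For last dose on Day d and a discontinuation visit t days later,

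gap = max(0, 114 − (d + t + 30)) = max(0, 84 − d − t).

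The gap is largest at t = 0. The last column counts the scheduled contacts on Days 30, 57 and 84 that fall after Day d.

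| Last dose, Day d | Gap at t = 0 (days) | Scheduled contacts lost before Visit 301 |
|---|---|---|
| 1 | 114 − 31 = 83 | 3 |
| 30 | 114 − 60 = 54 | 2 |
| 57 | 114 − 87 = 27 | 1 |
| 84 | 114 − 114 = 0 | 0 |

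Each day of delay in the discontinuation visit takes one day off the gap. The documents give no typical delay, so only the upper bound is stated. The lower bound is zero at any d if the final contact for early discontinuers is read from Protocol 3.1, which places it 30 days after last treatment; Table 5-4 instead lists the 30-day contact and Visit 301 on Day 114 separately and marks survival status at both.

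**Step 4: SAE reporting.** Protocol 5.6.2 sets the required collection as "adverse event and serious adverse events for up to 30 days after drug discontinuation". Section 7.2.2 extends SAE reporting to 30 days after last dose or last visit, whichever is later, and Table 5-4 marks AE and SAE review at the scheduled contacts and at Visit 301. A patient who stays can therefore have a later cut-off. For example, with last dose and discontinuation visit both on Day 1, the window ends on Day 1 + 30 = Day 31. If the Day 84 contact counts as that patient's last visit, it ends on Day 84 + 30 = Day 114. The documents do not say whether a telephone contact counts, so this is a possibility and not a fixed loss.

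**Step 5: disposition.** Table 5-4 separates the end of study treatment page from the row "Record end of treatment epoch disposition", which is marked under premature study discontinuation. SAP 2.3.1 says that, for each epoch, "the overall number of patients who entered, completed, and discontinued that phase will be summarized including the reasons for discontinuation". A study exit recorded under 5.4 could enter that table where the same event handled under 5.6.2 would not. The count of premature treatment discontinuations in SAP 2.4.1.1 is the same either way.

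**Step 6: analyses.** Protocol Section 9 excludes off-treatment measurements from every efficacy evaluation. SAP 2.8.2 counts treatment-emergent AEs to 7 days after last dose, and SAEs to 30 days. SAP 2.8.3 summarises deaths from events that start by last dose + 30 days, and lists all deaths in the database. An event that starts inside the window and later proves fatal would belong in the summary, but 7.2.2 requires progression of an SAE to be reported whenever it occurs. Survival status collected later would therefore mainly add to the listing.

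**The case against.** The strongest reply is that the documents nearly settle the matter themselves. Section 5.4 has a single sentence at the end of a section on blinding methods, while 5.6.2 is the dedicated section, names this exact event, and says that stopping drug is not withdrawal. On an ordinary reading the specific rule governs, and the reference to the trial in 5.4 could be taken as loose wording for study drug. This explains why 5.4 is the sentence to change. It does not remove the conflict: the protocol itself distinguishes stopping drug from leaving the study, the 5.4 instruction is mandatory, and no precedence is stated.

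A second reply concerns disposition and has force. The notes to Table 5-4 include an asterisked line limiting something to patients who withdrew consent, were lost to follow-up or died. The place it attaches to is not visible in the text available, but the premature study discontinuation column is the most plausible one. If so, a code break alone does not open that path. A reader might infer that disposition will certainly be counted differently from site to site; the documents support only that it might.

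A third reply is that the range of days is wide and its zero bound comes from a separate ambiguity about the final contact, which a change to 5.4 leaves in place. That is correct, and it is why no single figure is offered.

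**Conclusion.** The conflict is real and Section 5.4 is wrong as written; severity is low. Followed literally, it would drop the scheduled contacts and their AE and SAE review, could shorten SAE reporting, would omit required survival status, and might produce a study exit that 5.6.2 would not. Follow-up lost per patient lies between none and 83 days. The upper figure assumes last dose and discontinuation visit on Day 1, Visit 301 on Day 114, and 30-day safety follow-up kept under both sentences. The number of patients affected is unknown.

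Two stronger inferences are not supported. A reader might suppose that the primary or key secondary result is at risk; off-treatment measurements are not used for efficacy, so it is not. A reader might also suppose that Sections 5.5.5 and 5.5.9 and WTH06A positively contradict 5.4; they require only that drug stop and say nothing on participation. The opposite simplification, that safety collection is identical under either sentence, fails too, because of the later-of rule in 7.2.2 and the reviews marked in Table 5-4.

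**What to change.** In Protocol Section 5.4, replace the words that remove the patient from the trial with: *will be discontinued from double-blind study medication and asked to remain in the study for follow-up per Section 5.6.2*. Sections 5.5.5, 5.5.9 and 5.6.2 and SAP deviation WTH06A can stand as they are for this purpose.

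The cost is one phrase at the next amendment. Data collection forms and analyses do not change.

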5.5 Treating the patient

Sponsor qualified medical personnel will be readily available to advise on trial related medical questions or problems.

5.5.1 Patient numbering

Each patient is uniquely identified by a Patient Number which is composed by the site number assigned by Novartis and a sequential number assigned by the investigator. Once assigned to a patient, the Subject Number will not be reused.

Upon signing the informed consent form, the patient is assigned the next sequential number by the investigator. The investigator or his/her staff will contact the IRT and provide the requested identifying information for the patient to register them into the IRT. The site should select the electronic Case Report Form (eCRF) book with a matching Patient Number from the electronic data capture (EDC) system to enter data.

If the patient fails to be treated for any reason, the IRT must be notified within 2 days that the patient was not treated. The reason for not being treated will be entered on the eCRF.

5.5.2 Dispensing the study drug

Each study site will be supplied by Novartis with study drug in packaging of identical appearance.

The study drug packaging has a 2-part label. A unique medication number is printed on each part of this label which corresponds to one of the investigational drugs. Investigator staff will identify the study drug package(s) to dispense to the patient by contacting the IRT and obtaining the medication number(s). Immediately before dispensing the package to the patient, investigator staff will detach the outer part of the label from the packaging and affix it to the source document (Drug Label Form) for that patient's unique subject number.

5.5.3 Handling of study and additional treatment

5.5.3.1 Handling of study treatment

Study treatment must be received by a designated person at the study site, handled and stored safely and properly, and kept in a secured location to which only the investigator and designees have access. Upon receipt, all study treatment should be stored according to the instructions specified on the labels. Clinical supplies are to be dispensed only in accordance with the protocol. Technical complaints are to be reported to the respective Novartis Country Pharma Organization (CPO) Quality Assurance.

Medication labels will be in the local language and comply with the legal requirements of each country. They will include storage conditions for the study treatment but no information about the patient except for the medication number.

The investigator must maintain an accurate record of the shipment and dispensing of study treatment in a drug accountability log. Monitoring of drug accountability will be performed by monitors during site visits or remotely and at the completion of the trial. Patients will be asked to return all unused study treatment and packaging at the end of the study or at the time of discontinuation of study treatment.

5.5.3.2 Handling of additional treatment

The following non-study drug will be monitored as follows:

The non-study drug must be received by a designated person at the study site, handled and stored safely and properly, and kept in a secured location to which only the investigator and designees have access. Clinical supplies are to be dispensed only in accordance with the protocol.

The investigator must maintain an accurate record of the shipment and dispensing of the non-study drug in a drug accountability log. Monitoring of drug accountability will be performed by monitors during site visits or remotely and at the completion of the trial. Patients will be asked to return all unused non-study drug and packaging at the end of the Run-in for the Run-in medication and at the end of the study or at the time of discontinuation of study drug for the rescue medication.

These medications are:

- Salbutamol (100 microgram) or albuterol (90 microgram) used as rescue medication from Visit 1 to Visit 204;
- Fluticasone propionate (100 microgram b.i.d. or acceptable dose equivalent as outlined in Section 3.1 used as Run-in medication from Visit 101 to Visit 102.

